[Part 2 of 2 of the document. The other parts are not shown.]

Subjects should be registered in the study after the Investigator has verified that they are eligible per the criteria in Section 8.1 and Section 8.2 and all baseline assessments have been performed. No subject may begin treatment prior to enrollment and registration.

As confirmation, the Investigator will be provided with written verification of the subject's registration by mail or fax.

Refer to the Study Reference Manual for details on registration.

CONFIDENTIAL

The information contained herein may not be used, disclosed, or published without the written consent of Biogen MA Inc.

10. STUDY TREATMENT MANAGEMENT

Study treatment (PFS or autoinjectors) must be stored in a secure location. Accountability for study treatment is the responsibility of the Investigator. Study treatment must only be dispensed by a Pharmacist or medically qualified staff, and stored in a secure, monitored, locked location in accordance with the conditions specified in current prescribing information or the Directions for Handling and Administration (DHA) included in the Study Reference Manual.

Study treatment is to be dispensed only to subjects enrolled in this study. Once treatment is dispensed to a subject, it can only be used by that subject.

10.1. DAC HYP

Prefilled Syringe

DAC HYP is supplied as a liquid in a 1-mL BD-staked PFS with a 29 gauge × ½ inch needle, comprising 150 mg/mL DAC HYP plus excipient materials (sodium succinate, sodium chloride, and polysorbate 80). At a minimum, the study treatment label will include a study reference code, drug identifier, quantity of dosage units, lot number, and other pertinent information in accordance with local law. Depending on country requirements, the Investigator's name may also appear on the label. DAC HYP must not be used after the expiration date unless a written notification of an expiration date extension is provided by Biogen.

Autoinjector

The DAC HYP PFS is assembled inside a single-use, disposable autoinjector device.

The autoinjector label will include the DAC HYP product code "BIIB019," conditions for storage, Sponsor, and a caution statement. Depending on country requirements, the Investigator's name may also appear on the label. DAC HYP must not be used after the expiration date unless a written notification of an expiration date extension is provided by Biogen.

10.2. DAC HYP Preparation

Each DAC HYP PFS or autoinjector contains only one dose and is intended for SINGLE USE INJECTION ONLY. Any drug that remains in the PFS after injection must not be used for another dose or another subject.

After Week 12, subjects may choose to administer their DAC HYP dose at home, either by administering the injection themselves or by a designated caregiver. The subject or designated caregiver will be trained by clinic staff on the correct PFS injection technique prior to initiating at-home DAC HYP dosing.

Autoinjectors may be provided to selected sites and will be supplied injection-ready. Study personnel or subjects at these sites do not need to insert the PFS into the device. Study site personnel will receive appropriate autoinjector training from a Sponsor-designated trainer prior to initiation of autoinjector use.

CONFIDENTIAL

The information contained herein may not be used, disclosed, or published without the written consent of Biogen MA Inc.

10.3. DAC HYP Accountability

The study site must maintain accurate records demonstrating dates and amount of study treatment received, to whom dispensed (subject-by-subject accounting), any amount returned by subject, and accounts of any study treatment accidentally or deliberately destroyed.

Unless otherwise notified, all PFS and autoinjectors, both used and unused, must be saved for study treatment accountability. At the end of the study, a final reconciliation must be made between the amount of study treatment supplied, dispensed, and subsequently destroyed or returned to Biogen.

A written explanation will be provided for any discrepancies. After reconciliation, the Investigator must destroy or return to Biogen all unused study treatment PFS and autoinjectors as instructed by Biogen.

If any study treatment supplies are to be destroyed at the site, the Principal Investigator(s) must obtain prior approval by Biogen. The Principal Investigator(s) must notify Biogen, in writing, of the method, date, and location of destruction.

CONFIDENTIAL

The information contained herein may not be used, disclosed, or published without the written consent of Biogen MA Inc.

11. TREATMENT OF SUBJECTS

Biogen will provide DAC HYP (PFS or autoinjectors) to all study sites.

Refer to Section 10 (Study Treatment Management) for specifics on the preparation, storage, handling, disposal, and accountability of study treatment.

11.1. Study Treatment Schedule and Administration

All subjects will receive one DAC HYP 150 mg SC injection every 4 weeks.

DAC HYP will be administered by clinic staff at the monthly visits for the first 12 weeks of this study. After Week 12, administration of DAC HYP may occur in the clinic or at home (by the subject or by a designated caregiver) depending on subject preference. The subject or designated caregiver will be trained by clinic staff on the correct injection technique prior to initiating at-home DAC HYP dosing. **Subjects who are dosing at home must be instructed to not administer their monthly dose of DAC HYP until the study site has contacted them to authorize dosing. A window of ± 4 days applies to home dosing.**

Before a monthly dose of DAC HYP is given, LFT results from a prior test performed within the previous 28(+4) days must be reviewed by the *Study Neurologist* or their backup. Study personnel should promptly inform the subject whether the monthly dose of DAC HYP should be administered or whether study treatment is to be withheld based on the dosing criteria defined in Section 11.7.2. Study personnel will document this communication with the subject. Subjects should administer DAC HYP as soon as permission has been given as per the dosing schedule. Subjects need to record the date and time of dosing in their diary if they are dosing at home.

11.2. Placebo or Reference Product Agents

Not applicable.

11.3. Treatment Precautions

Anaphylactic-like and hypersensitivity reactions following administration of proteins such as DAC HYP can occur. DAC HYP will be administered in the clinic under observation by qualified medical personnel for the first 12 weeks of this study. Subjects will be educated by the *Study Neurologist* or their back-up on the signs and symptoms of hypersensitivity reactions and instructed to contact the site if they experience any acute or delayed reactions post injection.

11.4. Treatment Compliance

Compliance with treatment dosing is to be monitored and recorded by study site staff.

After Week 12, subjects who choose to administer their DAC HYP dose at home will record treatment in a dosing diary. The diary will be reviewed periodically by study site staff and the Clinical Monitor throughout the study. Subjects who choose at-home administration will return used PFS or autoinjectors to the clinic at their scheduled clinic visits.

CONFIDENTIAL

The information contained herein may not be used, disclosed, or published without the written consent of
Biogen MA Inc.

11.5. Concomitant Therapy

A concomitant therapy is any drug or substance administered from the Baseline/Entry Visit until completion of the study. A concomitant procedure is defined as any therapeutic intervention (e.g., surgery/biopsy, physical therapy) or diagnostic assessment (e.g., blood gas measurement, bacterial cultures) performed from the time the subject is enrolled in the study until the subject's final clinic visit.

Concomitant treatment with any of the following is not allowed during the study, unless approved by the Biogen Medical Director(s) or the Advisory Committee, or as otherwise described in this protocol:

- Any alternative disease modifying MS drug treatment such as chronic immunosuppressant therapy or other immunomodulatory treatments (including, but not limited to: IFN- β , IFN- α , glatiramer acetate, cyclophosphamide, methotrexate, mycophenolate mofetil, mitoxantrone, cyclosporine, azathioprine, or related products).
- Any investigational product, including investigational symptomatic therapies for MS and investigational therapies for non-MS indications.
- Any monoclonal antibodies other than DAC HYP.
- Intravenous immunoglobulin (IVIg), plasmapheresis or cytopheresis, total lymphoid irradiation, or T-cell or T-cell receptor vaccination.
- Any systemic steroid therapy including, but not limited to, oral corticosteroids (e.g., prednisone) or periodic (e.g., monthly) treatment with IV methylprednisolone (IVMP), except for protocol-defined treatment of relapses as described in [Section 14.6](#) or for limited, acute treatment of general medical conditions as per the discretion of *Study Neurologist*. Steroids that are administered by non-systemic routes (e.g., topical, inhaled) are allowed.
- Antineoplastic or chemotherapeutic agents, including, but not limited to, cyclophosphamide, methotrexate, azathioprine, cladribine, cytarabine, or flutamide.
- Valproic acid, carbamazepine, lamotrigine, or phenytoin. Subjects who have been taking 1 of these medications at a stable dose for at least 6 consecutive months may continue to receive the medication and may continue study treatment under this protocol. However, if any of these medications must be initiated or dose escalated, study treatment must be permanently discontinued as described in [Section 11.8](#).

Subjects who have been treated with any of these medications (which have not been approved by the Biogen Medical Director[s]) for fewer than 6 consecutive months, or who take more than 1 of these medications, or who have had dose escalations within the past 6 months must do 1 of the following:

- Discontinue the medication (any agent used for <6 consecutive months must be discontinued). Subjects may use an alternative medication allowed by the protocol, if needed.

CONFIDENTIAL

The information contained herein may not be used, disclosed, or published without the written consent of Biogen MA Inc.

- Subjects taking more than 1 agent must reduce to ≤ 1 agent (any agent that is continued must have been taken for at least 6 consecutive months).
- In the case of dose escalation, revert to a previous dose that had been used for at least 6 months.
- Permanently discontinue study treatment.
- Isoniazid, propylthiouracil, or nimesulide. Subjects who currently take any of these medications must either change to an alternative medication allowed by the protocol or permanently discontinue study treatment.

Subjects who receive any of these restricted medications may be required to permanently discontinue study treatment as outlined in Section 11.8. Subjects who permanently discontinue study treatment will be allowed to receive IVMP as treatment for MS relapse while they are participating in the study, as described in Section 11.8.

Use of the following medications is strongly discouraged during the study:

- Herbal or dietary supplements.
- Agents that have established risks of hepatotoxicity or serious rash according to labeling information (examples include, but are not limited to, amoxicillin/clavulanate, clarithromycin, ketoconazole, minocycline, nitrofurantoin, trimethoprim/sulfamethoxazole, diclofenac, sulfasalazine, amiodarone, methyldopa, nefazodone, and halothane). Alternatives to these therapies should be used whenever possible.

Symptomatic therapy, such as treatment for spasticity, depression, or fatigue is not restricted, but should be optimized as early as possible in an attempt to maintain consistent treatment for the duration of the study. Initiation of Fampridine-SR after enrollment is permitted, including when it is used in the acute management of protocol-defined relapse (as described in Section 14.6).

Subjects should be instructed not to start taking any new medications, including non-prescribed medications, unless they have received permission from the Investigator. The use of live vaccines in humans concurrently treated with daclizumab has not been explored; therefore live vaccines should not be administered to MS subjects who are being treated with DAC HYP.

The use of concomitant therapies or procedures defined in this section must be recorded on the subject's case report form (CRF), according to instructions for CRF completion (Note: concomitant therapies in the parent study that continued at Study 205MS303 entry must be recorded on the CRF). AEs related to administration of these therapies or procedures must be documented on the appropriate CRF. For subjects who prematurely discontinue study treatment, all concomitant medications should be recorded throughout the remainder of the subject's participation in the study.

11.6. Continuation of Treatment

No further provisions are made for access to the study treatment. If DAC HYP is proven to be beneficial, all regulatory requirements regarding poststudy access will be met.

CONFIDENTIAL

The information contained herein may not be used, disclosed, or published without the written consent of
Biogen MA Inc.

11.7. Treatment Schedule Modifications

Subjects who experience a significant change in their medical status (e.g., neurological worsening/suspected MS relapse, possible injection-site reaction, infection, cutaneous event, fever, abdominal pain, persistent diarrhea, jaundice, nausea, vomiting, pruritus) must contact the *Study Neurologist* as soon as possible and no more than 48 hours after symptom onset. The subject should then be evaluated by the *Study Neurologist* within no more than 72 hours for physical and neurological assessments and further treatment recommendations if appropriate. These subjects should not administer additional DAC HYP until they have been evaluated by the *Study Neurologist* or their backup.

Unscheduled PK/■ Visit (Table 6) can be performed in subjects who have evidence of significant changes in their medical conditions (as assessed by the Investigator). This visit must be approved by the Biogen Medical Director in advance.

Additional treatment considerations for specific events are described below.

11.7.1. Infections

Subjects who have evidence of a clinically significant infection will be instructed to notify the *Study Neurologist* or their backup within 48 hours of onset, and scheduled dosing of DAC HYP may be withheld. If the subject's infection resolves within 2 weeks of the scheduled DAC HYP dose, the subject may receive the previously scheduled dose of DAC HYP at that time. If the infection has not resolved within the 2 weeks, dosing of DAC HYP will remain suspended, and the subject will miss dosing until the infection is resolved.

11.7.2. Elevated Liver Function Tests

Before a monthly dose of DAC HYP is given, LFT results from a prior test (performed within 28[+4] days) must be reviewed by the *Study Neurologist* or their backup, and must be within the protocol-required limits shown below (LFT procedures are described in Section 14.4.3).

Study treatment *must be temporarily suspended* if a subject develops any of the following:

- ALT/SGPT or AST/SGOT $>3\times$ ULN
- any other clinically significant hepatic condition in the opinion of the Investigator including jaundice

Note: For subjects who present with jaundice, an LFT *must* be performed as soon as possible.

After a suspension, dosing of DAC HYP may be resumed when ALT/SGPT and AST/SGOT are $<2\times$ ULN provided that the criteria for permanent discontinuation have not been met (see Section 11.8).

Study treatment *must be permanently discontinued* if a subject develops any of the following:

- ALT/SGPT or AST/SGOT elevation $>8\times$ ULN that is confirmed by a repeat test (preferably within 24 hours)
- ALT/SGPT or AST/SGOT $>5\times$ ULN for more than 2 weeks

CONFIDENTIAL

The information contained herein may not be used, disclosed, or published without the written consent of Biogen MA Inc.

- ALT/SGPT or AST/SGOT $>3\times\text{ULN}$ with concomitant elevation of total bilirubin $>2\times\text{ULN}$
- If a subject has treatment suspended for an LFT elevation and has also had a prior treatment suspension for an LFT elevation during DAC HYP use, DAC HYP must be permanently discontinued unless an alternative explanation for the LFT elevation unrelated to DAC HYP use is clearly identified by the Investigator.

All subjects with elevated LFTs (**ALT/SGPT or AST/SGOT $>3\times\text{ULN}$**) should be managed per the guidelines below.

- Study treatment must be temporarily suspended and LFT elevation should be confirmed as soon as possible but no later than a week by a repeat test performed at the central laboratory. In cases where LFTs cannot be performed via the central laboratory, repeat LFT results from local laboratory can be used for confirmation.
- All subsequent testing after a treatment suspension or discontinuation is required to be performed centrally *at least weekly* until the LFT elevation has resolved.
- In subjects with treatment suspension or discontinuation, DAC HYP treatment may resume if a laboratory error is documented upon repeat testing OR when ALT/SGPT and AST/SGOT are $<2\times\text{ULN}$ provided that the criteria for permanent discontinuation have not been met (see Section 11.8).
- A careful review of all concomitant medications must be documented. The Investigator should consider discontinuation of all potential hepatotoxic medications. All recently started or non-essential concomitant medications should be suspended until the LFT elevation has resolved.
- An Unscheduled Hepatic Assessment Visit as soon as possible but within 7 days should be performed in the event of permanent discontinuation due to elevated LFTs (see Table 6).
- Subjects should be referred to a hepatic specialist if medically indicated.
- The LFT elevation that led to treatment discontinuation should continue to be monitored until LFT elevation has resolved.
- For subjects with initial **ALT/SGPT or AST/SGOT $>3\times\text{ULN}$ and concomitant elevation of total bilirubin $>2\times\text{ULN}$** :
 - *Permanently discontinue* DAC HYP and monitor until the LFT elevation has resolved.
- For subjects with initial **ALT/SGPT or AST/SGOT $>5\times\text{ULN}$ but $\leq 8\times\text{ULN}$** :
 - *Suspend dosing* and confirm as soon as possible but no later than a week.
 - For subjects with ALT/SGPT or AST/SGOT $>5\times\text{ULN}$ for more than 2 weeks:
 - *Permanently discontinue* DAC HYP and monitor until the LFT elevation has resolved.

CONFIDENTIAL

The information contained herein may not be used, disclosed, or published without the written consent of Biogen MA Inc.

- For subjects with **ALT/SGPT or AST/SGOT >8×ULN**:
 - *Suspend dosing* and confirm by a repeat test (preferably within 24 hours).
 - **If AST/SGOT >8×ULN in repeat test:** *Permanently discontinue* DAC HYP and monitor until the LFT elevation has resolved.
- For subjects with **ALT/SGPT or AST/SGOT >10×ULN not resolving for more than 2 weeks**:
 - *In consultation with the hepatic specialist*, a full evaluation of alternative causes of liver injury should be performed, and if testing for viral hepatitis is negative, LFT elevations are not improving, DAC HYP is suspected as the cause of the LFT elevation, and there are no known contraindications for corticosteroids, then, in continued consultation with the hepatic specialist, empiric treatment with systemic corticosteroids should be considered.

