11.8. Discontinuation of Study Treatment

A subject *must* permanently discontinue DAC HYP for any of the following reasons:

- The subject becomes pregnant. Study treatment must be discontinued immediately. Report the pregnancy according to the instructions in Section 15.5.4.
- The subject experiences a hypersensitivity or suspected allergic reaction (e.g., anaphylaxis and anaphylactoid reactions) to study treatment.
- The subject develops a chronic viral infection (e.g., hepatitis C, HIV).
- The subject develops elevated LFTs that meet any of the following criteria:

CONFIDENTIAL

The information contained herein may not be used, disclosed, or published without the written consent of Biogen MA Inc.

- The subject develops an ALT/SGPT or AST/SGOT elevation $>8\times$ ULN that is confirmed by a repeat test (preferably within 24 hours). This requires *immediate* discontinuation of DAC HYP, and treatment may not resume unless a laboratory error is documented upon repeat testing.
- ALT/SGPT or AST/SGOT $>5\times$ ULN for more than 2 weeks
- ALT/SGPT or AST/SGOT $>3\times$ ULN with concomitant elevation of total bilirubin $>2\times$ ULN at any time unless a laboratory error is documented upon repeat testing
- If a subject has treatment suspended for an LFT elevation and has also had a prior treatment suspension for an LFT elevation during DAC HYP use, DAC HYP must be permanently discontinued unless an alternative explanation for the LFT elevation unrelated to DAC HYP use is clearly identified by the Investigator.
- The LFT abnormality that led to treatment discontinuation should continue to be monitored until resolution is documented. An Unscheduled Hepatic Assessment Visit is needed in the event of permanent discontinuation due to elevated LFTs (see Section 11.7.2).

In addition, a careful review of all concomitant medications must be documented. The Investigator should consider discontinuation of all potential hepatotoxic medications. The subject should be referred to a physician with expertise in the diagnosis and treatment of liver disease, and additional hepatic studies should be performed according to local standard of care. The central laboratory may be utilized for additional hepatic testing per Investigator request.

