Follow-up visits will take place at 8, 12, 16, and 24 weeks after each subject's last dose of DAC HYP. Unscheduled Relapse Assessment Visits (if necessary) should be scheduled within 72 hours of the onset of any new neurological symptoms that may indicate neurological worsening or possible clinical relapse. Unscheduled Hepatic Assessment Visits (if necessary) should be scheduled as soon as possible (but within 1 week) following discontinuation of study treatment due to elevated LFTs. Unscheduled Dermatology Assessment Visits will be performed as per Section 11.7.3.

CONFIDENTIAL

The information contained herein may not be used, disclosed, or published without the written consent of
Biogen MA Inc.

Unscheduled PK/■ Visits should be scheduled as soon as possible following significant changes in subjects' medical conditions, as assessed by the Investigator. This visit must be approved by the Biogen Medical Director in advance.

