14.8. Unscheduled Hepatic Assessment Visit

The following tests/assessments will be performed as soon as possible (but within 7 days) after discontinuation of study treatment for subjects who are required to discontinue dosing due to elevated LFTs as described in Table 6 and Section 11.8.

- Physical examination and vital signs
- Comprehensive hepatic panel
- Recording of concomitant therapy
- Monitor and record AE/SAEs
- Protocol compliance and DAC HYP accountability
- LFTs (ALT/SGPT, AST/SGOT, alkaline phosphatase, total bilirubin, and GGT only)

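### Protocol 11.7.2: the >8×ULN branch is entered on ALT or AST, but its repeat-test discontinuation step names AST only

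*Protocol*

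**What the plan says.** The current protocol states the >8×ULN rule in three places.

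- **11.7.2, mandatory list.** Treatment must be permanently discontinued for "ALT/SGPT or AST/SGOT elevation $>8\times$ ULN that is confirmed by a repeat test".
- **11.8, mandatory list.** The same criterion appears, again for either enzyme. Here discontinuation is immediate, and dosing may not restart unless repeat testing documents a laboratory error.
- **11.7.2, management branch.** All subjects with ALT or AST >3×ULN "should be managed per the guidelines below". The relevant branch opens for subjects with "ALT/SGPT or AST/SGOT >8×ULN", suspends dosing and asks for a repeat test, preferably within 24 hours. Its next step is "If AST/SGOT >8×ULN in repeat test", followed by permanent discontinuation and monitoring to resolution.

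Two procedures depend on permanent discontinuation for elevated LFTs. The first is the Unscheduled Hepatic Assessment Visit, which 14.1 schedules "following discontinuation of study treatment due to elevated LFTs" and 14.8 requires "for subjects who are required to discontinue dosing due to elevated LFTs as described in Table 6 and Section 11.8". The second is the comprehensive hepatic panel in 13.2.

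**The concern.** The branch admits a subject on either enzyme but states its discontinuation trigger for one. A subject can enter on ALT, have ALT confirmed above 8×ULN with AST at or below it, and find no discontinuation instruction in the step meant to deal with the repeat result. The two mandatory lists do discontinue that subject.

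The line is operative text, because sites are directed to these steps once an elevation is found. It also belongs to a liver stopping rule in a programme whose background section (5.1, in the Version 2 text) reports more transaminase elevations and serious hepatic events on DAC HYP in Study 205MS301. At stake is whether a confirmed ALT-only case is promptly recognised as a permanent discontinuation, since that recognition triggers the hepatic visit (within 7 days) and the hepatic panel.

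**Working it through.** The plan gives no figure to reproduce and no formula applies. The check compares texts and counts provisions.

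**Step 1: the three statements by repeat-test result**

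| Repeat result | 11.7.2 list | 11.8 list | 11.7.2 branch |
|---|---|---|---|
| AST >8×ULN, any ALT | discontinue | discontinue | discontinue |
| ALT >8×ULN, AST ≤8×ULN | discontinue | discontinue | no instruction |
| Neither >8×ULN | not on this criterion | not on this criterion | not on this criterion |

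The texts diverge only in the second row.

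**Step 2: choice or slip?** The elevation thresholds in the current 11.7.2 are:

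- Lists and lead-in, 5: suspension at >3×; confirmed >8×; >5× for more than 2 weeks; >3× with bilirubin >2×; the >3× lead-in to the guidelines. All name ALT or AST.
- Branches, 6: >3× with bilirubin; >5× to ≤8×; >5× for more than 2 weeks; >8× entry; >8× repeat; >10×. Five name ALT or AST, and the >8× repeat names AST alone.

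Total 5 + 6 = 11, of which 10 name both enzymes and 1 names AST alone. The protocol gives no reason for confirming on AST only. The same line stands in 11.7.2 of Version 2, so it is not an artefact of reading the PDF.

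**Step 3: does the omission spread?** These provisions act on the classification:

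- Restart, 3: two statements in 11.7.2, each conditional on the 11.8 criteria not being met, and the bar on resumption in 11.8.
- Hepatic visit, 4: 11.7.2, 11.8, 14.1 and 14.8, all tied to discontinuation for elevated LFTs.
- Hepatic panel, 1: 13.2, tied to permanent discontinuation as defined in 11.7.2, whose mandatory list names ALT.

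Total 3 + 4 + 1 = 8, of which 0 name AST alone.

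**Step 4: what protects an ALT-only case if only the branch is read?**

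- Dosing is already suspended.
- LFTs are repeated centrally at least weekly until resolution (11.7.2).
- ALT >5×ULN for more than 2 weeks forces permanent discontinuation (11.7.2 and 11.8).
- A second suspension for LFT elevation during DAC HYP use does so too, unless an unrelated cause is clearly identified (11.7.2 and 11.8).
- Concomitant medications are reviewed, and specialist referral is made if medically indicated (11.7.2).
- An Adverse Event of Special Interest form is sent for each transaminase elevation (15.6).

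One path remains. Take a first suspension with no bilirubin criterion met, ALT confirmed >8×ULN, AST ≤8×ULN, and ALT down to 5×ULN or below within two weeks. No branch discontinues this subject; only the mandatory lists do. A site that did not consult them could miss the trigger for the visit and the panel.

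**The case against.** The strongest reply is that the step says what to do if AST is above 8×ULN; it does not say that discontinuation follows only in that case. It states a sufficient trigger and is silent on ALT, and silence in one sub-bullet does not contradict a rule stated twice in mandatory terms, once earlier in the same section. The lists use must and the branches use should. Section 11.1 sends staff to 11.7.2 as a whole for the dosing criteria. Harm therefore needs a reader who takes one line and skips both lists.

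Most of this stands. It rules out the stronger reading that a reader might infer, namely that the protocol lets a subject with confirmed ALT >8×ULN and lower AST stay on or return to DAC HYP. Nothing in the branch permits continuation. Restart needs both enzymes <2×ULN with the 11.8 criteria unmet (or a documented laboratory error), and 11.8 separately bars resumption after a confirmed >8×ULN in either enzyme.

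The reply does not make the line correct. The branch is the procedure that implements the rule, it is entered on ALT, and it then gives no answer for ALT. A stopping rule should not leave a site to reconcile its procedure with its criteria.

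**Conclusion.** The point holds as a minor drafting omission. The repeat-test step in the >8×ULN branch of 11.7.2 is inconsistent with its own entry condition and with the mandatory lists in 11.7.2 and 11.8. It affects 1 of 11 elevation thresholds and none of the 8 downstream provisions. The realistic consequence is a delayed hepatic visit and panel at a site using that line alone. The documents give no basis for a number of subjects or a length of delay. No endpoint, estimate or analysis changes.

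This rests on two assumptions. First, the mandatory lists take precedence. No sentence says so, but the must/should wording and the restart conditions make it a sound inference. Second, the current Table 6, which is not in the text at hand, agrees with the sections cited; its Version 2 counterpart (footnote 7) also ties the panel to 11.8.

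**What to change.** In the >8×ULN branch of 11.7.2, insert *ALT/SGPT or* before AST/SGOT in the repeat-test condition, so that it reads *If ALT/SGPT or AST/SGOT >8×ULN in repeat test*. Leave the instruction that follows unchanged: permanent discontinuation of DAC HYP and monitoring until the elevation has resolved. This brings the branch into line with both mandatory lists and creates no new conflict.

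The cost is two added words at the next amendment, with no new assessment and no change to any analysis.
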